### 6.6.1 Dose modifications

For participants who do not tolerate the protocol-specified dosing schedule, dose interruptions, and/or reductions are either recommended or mandated in order to allow participants to continue the study treatment.

These dose modifications are summarized in [Table 6-3](#). Deviations to mandatory dose interruptions and/or reductions are not allowed. Permanent discontinuation from study treatment is mandatory for specific events indicated as such in [Table 6-3](#) or listed in [Section 9.1](#).

These dose changes must be recorded on the appropriate eCRF.

Additionally dose escalations of antihyperglycemic medication as described in [Section 6.6.2](#) must also be recorded on the appropriate eCRF.

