Grade 3 (Increase of ≥7 stools per day over baseline; hospitalization indicated; severe increase in ostomy output compared to baseline; limiting self-care ADL)	
 
Omit dose until resolved to ≤ Grade 1, then decrease dose level.
 
Manage according to local standard of care medical management, including electrolyte monitoring, administration of antiemetics and antidiarrheal medicinal products and/or fluid replacement and electrolyte supplements, as clinically indicated.
 

Grade 4 (Life-threatening consequences; urgent intervention indicated)	
 
Discontinue participant from treatment.
 
Manage according to local standard of care medical management, including electrolyte monitoring, administration of antiemetics and antidiarrheal medicinal products and/or fluid replacement and electrolyte supplements, as clinically indicated.
 

Worst toxicity - CTCAE grade (value)	Dose Modifications for alpelisib
Investigations (Pancreatic)	
Pancreatitis	
Grade 2 or Grade 3	
 
Omit dose until resolved to Grade ≤ 1, then resume treatment at decreased dose level. If toxicity recurs, permanently discontinue participant from alpelisib
 

Skin and subcutaneous tissue disorders	
Consultation with a dermatologist is highly recommended for better assessment and management of alpelisib-induced skin toxicity (see Section 6.6.3.3 ). Dermatologist consultation is mandated for serious cutaneous reactions (i.e. fulfilling seriousness criteria for AE Reporting) and for severe cutaneous reactions like Stevens-Johnson-Syndrome, Toxic Epidermal Necrolysis, Erythema Multiforme, DRESS.	
Rash	
Grade 1 (< 10% BSA with active skin toxicity*)	
 
Maintain dose level.
 
Initiate topical corticosteroids 3-4 x daily, preferred compounds to use are triamcinolone, betamethasone for up to 28 days, as long as skin toxicity is active.
 
If active rash is not resolved within 28 days of appropriate treatment, add low dose systemic corticosteroid (20-40 mg/d), such as prednisone 10 mg 3 x daily.
 
 
For participants with symptoms like burning and/or pruritus add a non-sedating anti-histamine such as cetirizine once daily during daytime and a sedating antihistamine such as diphenhydramine once daily at night.

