## 8 Visit schedule and assessments

The Assessment Schedule [Table 8-2](#) lists all of the assessments when they are performed. All data obtained from these assessments must be supported in the participant's source documentation.

Treatment cycles are intended to be 4 weeks (28 days), but the treatment can be delayed in order to manage toxicities according to the alpelisib dose modification criteria in [Section 6.6.1.1](#) and

the locally approved label and local practice for fulvestrant, dapagliflozin + metformin XR, and metformin XR.

Participants should be seen for all visits/assessments as outlined in the assessment schedule [Table 8-2](#) or as close to the designated day/time as possible. Missed or rescheduled visits should not lead to automatic discontinuation.

Participants who discontinue from study treatment are to return for the end of treatment visit as soon as possible, and attend the follow-up visits as indicated in the Assessment Schedule.

Participants who discontinue from study or withdraw their consent/oppose the use of their data/biological samples should be scheduled for a final evaluation visit if they agree, as soon as possible, at which time all of the assessments listed for the final visit will be performed. At this final visit, all dispensed investigational product should be reconciled, and the adverse event and concomitant medications not previously reported must be recorded on the eCRF.

The “X” in the table denotes the assessments to be recorded in the clinical database or received electronically from a vendor. The “S” in the table denotes the assessments that are only in the participant’s source documentation and do not need to be recorded in the clinical database.

Additional visits may be needed based on the Investigator’s discretion and are permitted at any time throughout the study.

At this final visit, all dispensed investigational product should be reconciled, and the adverse event and concomitant medications should be up to date on the eCRF.

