## 9 Discontinuation and completion

### 9.1 Discontinuation from study treatment and from study

#### 9.1.1 Discontinuation from study treatment

Discontinuation of study treatment for a participant occurs when study treatment is permanently stopped for any reason (prior to the planned completion of study drug administration, if any) and can be initiated by either the participant or the Investigator.

The Investigator must discontinue study treatment for a given participant if, he/she believes that continuation would negatively impact the participant's well-being.

Discontinuation from study treatment is required under the following circumstances:

- Participant/guardian decision
- Pregnancy
- Use of prohibited treatment as per recommendations in the prohibited treatment [Section 6.2.2](#)
- Any situation in which continued study participation might result in a safety risk to the participant
- Adverse event or laboratory abnormalities requiring permanent discontinuation of study treatment as per [Section 6.6.3](#)
- Any laboratory abnormalities that in the judgment of the Investigator, taking into consideration the participant's overall status, prevents the participant from continuing participation in the study
- Progressive disease per RECIST 1.1 as per Investigator's assessment (see [Section 8.3](#)).
- Protocol deviation that results in significant risk to participant's safety
- Study terminated by sponsor

If discontinuation from study treatment occurs, the Investigator should make a reasonable effort to understand the primary reason for the participant's discontinuation from study treatment and record this information.

[figure not shown]
Participants who discontinue from study treatment agree to return for the end of treatment and follow-up visits indicated in the Assessment Schedule (refer to [Section 8](#)).

If the participant cannot or is unwilling to attend any visit(s), the site staff should maintain regular telephone contact with the participant, or with a person pre-designated by the participant. This telephone contact should preferably be done according to the study visit schedule.

After discontinuation from study treatment, at a minimum, in abbreviated visits, the following data should be collected at clinic visits or via telephone/email contact:

- New/concomitant treatments
- Adverse Events/Serious Adverse Events

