### **Diarrhea unresolved**

- If diarrhea still persisting (CTCAE grades 1 and 2), after 2x 24 hrs with high dose loperamide and opiates then admit to hospital and employ measures as for CTCAE grade 3 and 4 until diarrhea resolved.
- If diarrhea still persisting and progressed to CTCAE grades 3 and 4, employ measures described below.

#### Treatment of diarrhea CTCAE grade 3 or 4

Severe diarrhea CTCAE grade 3 or 4 may be treated with hospitalization, high dose loperamide (initial 4 mg, then 2 mg every 2 hrs and addition of opium tincture or dihydrocodeine tartrate tablets/injections, start of IV fluids and antibiotics as needed with monitoring of patients condition (to rule out dehydration, sepsis, ileus) medical check and workup (see section Diarrhea workup and additional test in the particular trial protocol). Observe patient for response.

After 12-24 hrs:

- If diarrhea persisting administer subcutaneous (s.c.) Sandostatin/octreotide (100-500 µg tid)
- Continue IV fluids and antibiotics as needed
- If diarrhea CTCAE grade 3 or 4 still persists patients should receive opium tincture or dihydrocodeine tartrate injections s.c. or i.m.
- If diarrhea CTCAE grade 3 or 4 is still persisting s.c. Sandostatin/octreotide (500-1000 µg TID) should be administered.
- To control and/or resolve diarrhea, next cycle of treatment should be delayed by 1 or 2 weeks. Treatment should be continued only when diarrhea resolved.

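### Grade 4 diarrhea: Table 6-3 ends treatment, while Appendix 2 delays the next cycle and allows treatment to continue once the diarrhea has resolved

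*Protocol*

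**What the plan says.** **Table 6-3, diarrhea rows.** The row headed "Grade 4 (Life-threatening consequences; urgent intervention indicated" carries the action "Discontinue participant from treatment" and has no restart rule. The Grade 3 row reads "Omit dose until resolved to ≤ Grade 1, then decrease dose level".

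**Section 9.1.1.** "Discontinuation of study treatment for a participant occurs when study treatment is permanently stopped for any reason". The glossary entry for discontinuation from study treatment says the same.

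**Section 6.6.1.** "Permanent discontinuation from study treatment is mandatory for specific events indicated as such in" Table 6-3 or listed in Section 9.1. Section 6.6.1.1 repeats this for alpelisib.

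**Appendix 2 (Section 16.2).** Under "Treatment of diarrhea CTCAE grade 3 or 4", the last of the steps for diarrhea not controlled after 12 to 24 hours says the "next cycle of treatment should be delayed by 1 or 2 weeks. Treatment should be continued only when diarrhea resolved". The block does not separate Grade 4 from Grade 3 and mentions neither discontinuation nor dose level.

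**Section 8.** Cycles are meant to last 28 days, "but the treatment can be delayed in order to manage toxicities". The sentence goes on to tie such delays to the alpelisib criteria in Section 6.6.1.1.

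**Section 6.3.2.1.** Alpelisib is taken daily, without a pause from one cycle to the next.

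**The concern.** One event has two instructions that cannot both be followed. Under Table 6-3 the participant stops. Under Appendix 2 the next cycle is postponed, and a postponed cycle presupposes that treatment starts again.

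What is at stake is mainly safety, because the row defines Grade 4 by life-threatening consequences. There is also a data-quality effect. Alpelisib discontinuation is a named intercurrent event of the primary estimand, and interruptions, reductions and exposure are tolerability endpoints (Section 2, Table 2-1). If sites handle the same event differently, those records are not comparable.

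**Working it through.** The plan gives no figure to reproduce for this point, so the check is a comparison of texts.

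**1. Instructions side by side**

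| | Table 6-3 | Appendix 2, Grade 3 or 4 block |
|---|---|---|
| Grade 4 | Discontinue; no restart rule | Delay next cycle 1 or 2 weeks; continue once resolved |
| Grade 3 | Hold to Grade 1 or less, then lower the dose level | Delay next cycle 1 or 2 weeks; continue once resolved; dose level not mentioned |

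At Grade 4 the actions are incompatible. At Grade 3 both texts hold drug and resume after improvement. They differ in the resumption threshold (Grade 1 or less against resolved), and Appendix 2 is silent on dose level.

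**2. Does any text settle which one governs?**
- Section 6.6.1 makes discontinuation mandatory where Table 6-3 so indicates, and the full Section 8 sentence sends delays to Section 6.6.1.1 and so to Table 6-3. Both point toward the table.
- The Grade 4 diarrhea row lacks the word *permanently*, which the Grade 4 bilirubin, AST/ALT and rash rows carry. Section 9.1.1 and the glossary largely fill that gap.
- Section 6.6.1.1 describes the content of Table 6-3 as recommendations and gives weight to the treating physician's judgment.
- Appendix 2 calls its algorithm recommended, but in the same paragraph calls proper management of diarrhea mandatory.
- Appendix 2 refers to Table 6-3 only for CTCAE grading. The diarrhea rows of Table 6-3 do not refer to Appendix 2.
- Section 9.1.1 sends discontinuation for adverse events to Section 6.6.3, which has no diarrhea subsection.

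The weight of the text favors Table 6-3, but a site that opens Appendix 2 is not told so.

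**3. Fit with dosing.** With uninterrupted daily alpelisib, postponing the next cycle does not say whether drug is stopped on the day of the event or only withheld at the next cycle boundary. Table 6-3 omits the dose at once.

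**4. Size.** Section 1.1.2.2 reports Grade 3 or higher diarrhea in 7% of the SOLAR-1 alpelisib plus fulvestrant arm, at a median follow-up of 42.4 months. Neither document splits Grade 3 from Grade 4. The Grade 4 rate therefore lies somewhere between 0% and 7% on that experience.

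**The case against.** The strongest reply is that precedence is already stated. Section 6.6.1 is mandatory, Section 8 routes delays through Section 6.6.1.1, and Appendix 2 reads as general compound-level guidance: it cites single-agent BYL719 studies and refers the workup to the particular trial protocol. Its sentence about continuing is also worded as a restriction, not as an order to restart. Much of this stands. A careful reader of the whole protocol would probably follow Table 6-3, so the most that can be said is that a site *could* resume. It does not remove the conflict, because Appendix 2 includes Grade 4 by name, presupposes a next cycle and does not send the reader to the table for action on study drug.

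Three stronger readings are tempting but not supported.

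- **About 9 of 132 participants face stop against resume.** The product 0.07 × 132 = 9.2 uses the Grade 3 or higher rate over long follow-up. It does not count Grade 4 events. Any increase from metformin XR in both arms is not quantified in the documents.
- **A delayed cycle stretches the eight-week primary-endpoint window.** Section 6.6.1.1 says planned assessments carry on while alpelisib is withheld. Nor does the nine-week follow-up after early stopping use a different end point. C3D8 is study day 2 × 28 + 8 = 64. Eight weeks from C1D8 is 8 + 56 = 64, and nine weeks from C1D1 is 1 + 63 = 64.
- **Appendix 2 rules out a dose decrease at Grade 3.** It is silent on dose level, and Table 6-3 covers it.

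The SAP (Sections 1 and 4) also reports early termination, drops the primary analysis and only lists exposure, so the analytic consequence is now small. The safety contradiction does not depend on any analysis.

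**Conclusion.** The contradiction at Grade 4 is real and should be corrected. Table 6-3 ends treatment, and Appendix 2, read as written, allows it to continue after resolution. Other sections suggest that the table governs, without Appendix 2 saying so. The Grade 3 difference and the poor fit of a cycle delay with continuous dosing are secondary.

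The number affected is unknown. It is a subset of those with Grade 3 or higher diarrhea, 7% in SOLAR-1, and using that figure assumes the SOLAR-1 rate carries over to this population. Sample size, power and the primary-endpoint window are not affected. The conclusion rests on two readings: that discontinuation in Table 6-3 has the permanent meaning given in Section 9.1.1 and the glossary, and that a delayed next cycle implies resumption. No view is taken on which clinical rule is right.

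**What to change.** Reconcile the diarrhea rows of Table 6-3 with the Grade 3 or 4 block of Appendix 2 so that each grade has one stop, hold and resume instruction. Alternatively, add a sentence to Appendix 2 stating which text governs action on study drug. In the same edit, use one resumption criterion at Grade 3, and either remove the cycle-delay wording or express it in terms that fit continuous alpelisib dosing. The sponsor's clinical team decides which rule is kept. The cost is a few lines of protocol text, with no new procedures or data collection.

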### 6.6.1.2 Fulvestrant dose modification

The established clinical dose of fulvestrant (500 mg) will be used in each arm and no dose modification of fulvestrant is planned in this study. For information on fulvestrant and management of related AEs refer to the Faslodex® summary of product characteristics (SmPC) or local Prescribing Information.

## 6.6.2 Dose titration guideline for antihyperglycemic agents

### 6.6.2.1 Dose titration guideline for metformin XR

The starting dose of metformin XR is 500 mg orally once daily with dinner.

Titrate to MTD over a period of 3 weeks as described in [Table 6-4](#).

**Table 6-4 Metformin XR Titration Recommendations**

Metformin XR Titration	Remarks
500 mg once daily with dinner	If no gastrointestinal intolerance after several days, increase to next level
1000 mg once daily with dinner	If tolerated, increase to next level
1500 mg once daily with dinner	If tolerated, increase to next level
2000 mg once daily with dinner	If not tolerated, reduce to prior tolerated dose.

If additional antihyperglycemic agents are required prior to Cycle 3 Day 8 to achieve adequate control of fasting blood glucose levels, it is recommended that participants randomized to the metformin XR arm avoid the use of SGLT2i, as this may impact the primary endpoint assessment. However, beyond Cycle 3 Day 8, SGLT2i are acceptable.

For additional information on metformin XR dosing and management of related AEs refer to the local Prescribing Information.

### 6.6.2.2 Dose titration guideline for dapagliflozin + metformin XR

The starting dose of dapagliflozin + metformin XR is 5 mg dapagliflozin + 500 mg metformin XR orally once daily. If tolerated after several days, increase to dapagliflozin 5 mg +1000 mg metformin XR once daily in the morning with food. If tolerated, increase to dapagliflozin 10 mg +1000 mg metformin XR once daily in the morning with food. If tolerated, increase to the maximum daily dose of dapagliflozin 10 mg + 2000 mg metformin XR once daily in the morning with food. If not tolerated, reduce to prior tolerated dose. Titrate to the MTD over a period of 3 weeks as described in [Table 6-5](#).

**Table 6-5 Dapagliflozin + Metformin XR Titration Recommendations**

Dapagliflozin + Metformin XR Titration	Remarks
5 mg dapagliflozin + 500 mg metformin XR once daily with breakfast	If tolerated after several days, increase to next level
5 mg dapagliflozin + 1000 mg metformin XR once daily with breakfast	If tolerated, increase to next level
10 mg dapagliflozin + 1000 mg metformin XR once daily with breakfast	If tolerated, increase to next level
10 mg dapagliflozin + 2000 mg metformin XR once daily with breakfast	If not tolerated, reduce to prior tolerated dose

In case of intolerance to either the dapagliflozin or metformin XR component of treatment, it is acceptable to continue monotherapy with dapagliflozin or metformin XR, as tolerated.

The risk of diabetic ketoacidosis (DKA) must be considered in the event of non-specific symptoms such as nausea, vomiting, anorexia, abdominal pain, excessive thirst, difficulty breathing, confusion, unusual fatigue or sleepiness. Participants should be assessed for ketoacidosis immediately if these symptoms occur, regardless of blood glucose level. In patients where DKA is suspected or diagnosed, treatment with dapagliflozin should be discontinued immediately.

The most common adverse reactions associated with dapagliflozin + metformin XR (5% or greater incidence) were female genital mycotic infection, nasopharyngitis, urinary tract infection, diarrhea, and headache.

Adverse reactions reported in > 5% of patients treated with metformin XR and more commonly than in patients treated with placebo are: diarrhea and nausea/vomiting.

A higher incidence of adverse reactions related to reduced intravascular volume and renal function has been observed in the specific population of patients with renal impairment receiving dapagliflozin + metformin XR. Therefore, in this study, those with moderate to severe renal impairment are not eligible for study participation. During course of the study, chemistry panels including creatinine will be obtained at regular interval, as per [Table 8-2](#). At the discretion of the investigator, further clinical evaluation may be needed for participants with observed increases in serum creatinine, which may be indicative of renal impairment.

For additional information on dapagliflozin + metformin XR and management of related AEs refer to the local Prescribing Information.

### **6.6.3 Follow-up for toxicities**

All participants must be followed up for safety (adverse events and serious adverse events) for 30 days following the last dose of study treatment.

Participants whose treatment is interrupted or permanently discontinued due to an adverse event or a clinically significant laboratory value must be followed until resolution or stabilization of the event, whichever comes first. Further guidelines and recommendations for the management of specific study treatment combination-induced toxicities are provided below.

### 6.6.3.1 Follow up on potential drug-induced liver injury (DILI) cases

Participants with transaminase increase combined with total bilirubin increase may be indicative of potentially severe DILI, and should be considered as clinically important events and assessed appropriately to establish the diagnosis. The required clinical information, as detailed below, should be sought to obtain the medical diagnosis of the most likely cause of the observed laboratory abnormalities.

The threshold for potential DILI may depend on the participant's baseline AST/ALT and total bilirubin value; participants meeting any of the following criteria will require further follow-up as outlined below:

- For participants with normal ALT and AST and total bilirubin value at baseline: AST or ALT  $> 3.0 \times$  upper limit of normal (ULN) combined with total bilirubin  $> 2.0 \times$  ULN without evidence of cholestasis
- For participants with elevated AST or ALT or total bilirubin value at baseline: [AST or ALT  $> 3.0 \times$  baseline] or [ALT or AST  $> 8.0 \times$  ULN], whichever occurs first, combined with [total bilirubin  $> 2.0 \times$  baseline AND  $> 2.0 \times$  ULN]

As DILI is essentially a diagnosis of exclusion, other causes of abnormal liver tests should be considered and their role clarified before DILI is assumed as the cause of liver injury.

A detailed history, including relevant information such as review of ethanol consumption, concomitant medications, herbal remedies, supplement consumption, history of any pre-existing liver conditions or risk factors, should be collected.

Laboratory tests should include ALT, AST, total bilirubin, direct and indirect bilirubin, gamma-glutamyl transferase (GGT), prothrombin time (PT)/INR, alkaline phosphatase (ALP), albumin, and creatine kinase. If available, testing of Glutamate Dehydrogenase (GLDH) is additionally recommended.

Evaluate status of liver metastasis (new or exacerbation) or vascular occlusion – e.g., using CT, MRI, or duplex sonography.

Perform relevant examinations (Ultrasound or MRI, Endoscopic retrograde cholangiopancreatography (ERCP)) as appropriate, to rule out an extrahepatic cause of cholestasis. Cholestasis (is defined as an ALP elevation  $> 2.0 \times$  ULN with R value  $< 2$  in participants without bone metastasis, or elevation of the liver-specific ALP isoenzyme in participants with bone metastasis).

Note: The R value is calculated by dividing the ALT by the ALP, using multiples of the ULN for both values. It denotes whether the relative pattern of ALT and/or ALP elevation is due to cholestatic ( $R \leq 2$ ), hepatocellular ( $R \geq 5$ ), or mixed ( $R > 2$  and  $< 5$ ) liver injury. For children, there are caveats to calculating the R-ratio as normal levels of ALP are higher than in adults with standard ranges varying by developmental age. In clinical situations where it is suspected that ALP elevations are from an extrahepatic source, the GGT can be used if available. GGT may be less specific than ALP as a marker of cholestatic injury, since GGT can also be elevated by enzyme induction or by ethanol consumption. It is more sensitive than ALP for detecting bile duct injury. [Table 6-6](#) provides guidance on specific clinical and diagnostic assessments which can be performed to rule out possible alternative causes of observed liver function test (LFT) abnormalities.

